8.2 Secondary Objective(s)

The secondary objectives of the study are:

1. To characterize the PK of perampanel and the relationship between perampanel plasma concentrations, efficacy, and safety using population PK/PD modeling.
2. To evaluate the effects of perampanel on cognition, behavior, visuomotor skills, and growth and development in children during short-term (23 weeks) and long-term (up to 52 weeks) treatment.
3. To evaluate the frequency of EEG abnormalities during awake and sleep state during 52 weeks of treatment.
4. To evaluate suicidal ideation and suicidal behavior in children 6 years to less than 12 years as measured by the Columbia-Suicide Severity Rating Scale (C-SSRS) during 52 weeks of treatment.
5. To evaluate the efficacy of perampanel as measured by the median percent change per 28 days in seizure frequency, by the proportion of responders ($\geq 25\%$, $\geq 50\%$, and $\geq 75\%$), and by the proportion of subjects who are seizure-free for POS, PGTC, and Generalized Tonic-Clonic (GTC) seizures.
6. To evaluate, in Japanese subjects, the efficacy of perampanel on POS in the present study as compared with placebo in Study E2007-J000-335.
7. To assess the effects of perampanel on the Clinical Global Impression (CGI), as measured by CGI of Change (CGIC). (revised per Amendment 04)

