9.1.2.1 Titration Period

During the Titration Period, subjects will be stratified by the presence or absence of concomitant EIAEDs and will be titrated using the dosing schedule based on individual clinical response and tolerability no more frequently than at weekly intervals, up to 8 mg/day for non-EIAED subjects or 12 mg/day for EIAED subjects. With the exception of subjects enrolled in Japan, EIAED subjects may titrate beyond 12 mg/day and up to 16 mg/day if they tolerate 12 mg/day and are deemed likely to benefit from a higher dose. Non-EIAED subjects may go beyond 8 mg/day and up to 12 mg/day if they tolerate 8 mg/day and are deemed likely to benefit from a higher dose. Subjects will be flexibly dosed based on individual tolerability. Regardless of EIAED status, subjects enrolled in Japan may not receive doses higher than 12 mg/day. The Titration Period is a duration of up to 11 weeks, during which multiple dose adjustments are allowed in order to identify each subject's optimum dose. All visits are to be done within ± 3 days of the schedule. Each study visit is based on the actual prior visit (eg, Visit 3 is completed 2 weeks ± 3 days of Visit 2, Visit 4 is completed 3 weeks ± 3 days of Visit 3, Visit 5 is completed 3 weeks ± 3 days of Visit 4). (revised per Amendment 02) Subjects will remain on their optimum dose once it is achieved during the Titration Period. (revised per Amendment 01) The dosing schedule is illustrated in [Table 1](#).

According to the investigator's clinical judgment, subjects experiencing intolerability at any dose may remain at the same dose or have their dose decreased 1 dose level down to the previously tolerated dose. If the subject continues to present significant intolerable AEs at the decreased dose and the investigator deems it is necessary, the dose can be decreased further to the next dose level down. Dose decreases can be done via telephone. Subjects whose dose has been decreased can have their dose increased again if tolerability improves; this can be done at the next clinic visit after the investigator has deemed it is appropriate in view of resolution of the AE(s). Multiple dose adjustments will be allowed during the Titration Period. Only upon completion of the 11 weeks Titration Period, subjects will enter the Maintenance Period. (revised per Amendment 01)

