9.1.2.2 Maintenance Period

During the Maintenance Period of the Core Study (up to 12-week), subjects will continue taking perampanel oral suspension once daily at the dose level they achieved at the end of the Titration Period. (revised per Amendment 02) Multiple dose adjustment is allowed if a subject is experiencing intolerable AE(s) or a higher dose is deemed to be beneficial. All visits are to be done within ± 7 days of the schedule. Each study visit is based on the actual prior visit (eg, Visit 6 is completed 3 weeks ± 7 days of Visit 5, Visit 7 is completed 4 weeks ± 7 days of Visit 6, Visit 8 is completed 4 weeks ± 7 days of Visit 7, Visit 9 is completed 4 weeks ± 7 days of Visit 8). (revised per Amendment 02)

During the Titration and Maintenance Periods, all dose adjustments will be done via 1 dose level up or down. Those who cannot tolerate a minimum of 2 mg dose must discontinue from the study.

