9.5.2 Schedule of Procedures/Assessments – Core Study

9.5.2.1 Schedule of Procedures/Assessments

[Table 4](#) presents the schedule of procedures/assessments for the Core Study.

Table 4 Schedule of Procedures/Assessments in Study E2007-G000-311: Core Study

Phase	Pre-Treatment	Treatment Phase									Early Discontinuation ^d	Unscheduled
	Screening/Baseline	Titration ^a				Maintenance ^b				Follow-up ^{b,c}		
Visit	1	2	3	4	5	6	7	8	9			
Week	From up to -4 weeks ±3 days to Week 0 (outside of Japan) -4 weeks ±3 days to Week 0 (Japan only) (revised per Amendment 02)	0	2	5	8	11	15	19	23	27		
Procedures/Assessments												
Demography	X											
Informed consent/assent	X											
Inclusion/exclusion criteria	X	X										
Medical history	X											
Epilepsy medical history	X											
Prior/concomitant medication(s)	X	X	X	X	X	X	X	X	X	X	X	X
Prior/concomitant AED(s)	X	X	X	X	X	X	X	X	X	X	X	X
Neurological examination ^e	X								X	X	X	
Physical examination ^e	X								X	X	X	
Vitals ^f and weight ^g	X	X	X	X	X	X	X	X	X	X	X	X
Height ^g		X							X		X	
Adverse events	X	X	X	X	X	X	X	X	X	X	X	X
Study drug compliance			X	X	X	X	X	X	X		X	X
Dispense study drug		X	X	X	X	X	X	X	X ^h			X ⁱ
Retrieve unused study drug			X	X	X	X	X	X	X		X	X ⁱ
Dispense subject's diary	X	X	X	X	X	X	X	X	X ^h			X
Retrieve and review diary		X	X	X	X	X	X	X	X	X	X	X
Clinical laboratory tests ^j	X ^k					X			X ^k	X	X	X

Table 4 Schedule of Procedures/Assessments in Study E2007-G000-311: Core Study

Phase	Pre-Treatment	Treatment Phase									Early Discontinuation ^d	Unscheduled
		Screening/Baseline	Titration ^a				Maintenance ^b			Follow-up ^{b,c}		
Visit	1	2	3	4	5	6	7	8	9			
Week	From up to -4 weeks ±3 days to Week 0 (outside of Japan) -4 weeks ±3 days to Week 0 (Japan only) (revised per Amendment 02)	0	2	5	8	11	15	19	23	27		
Procedures/Assessments												
Thyroid (TSH, fT3, fT4) and IGF-1 testing	X								X		X	
Serum β-hCG (or hCG) test ^l	X											
Urine pregnancy test ^l		X	X	X	X	X	X	X	X	X	X	X
C-SSRS ^m	X	X	X	X	X	X	X	X	X	X	X	X
12-lead ECG ⁿ	X								X	X	X	X ^o
EEG ^p	X								X		X	X ^o
Perampanel PK sampling (plasma) ^{q,r}							X	X	X		X	X
Telephone call ^s		X	X	X	X	X	X	X				
ABNAS ^t	X ^u	X					X		X		X ^v	
Lafayette Grooved Pegboard Test	X ^u	X					X		X		X ^v	
Child Behavior Checklist		X							X		X	
EQ-5D-Y		X							X		X	
Clinical Global Impression		X							X		X	
Disposition		X							X		X	
IxRS	X	X	X	X	X	X	X	X	X	X	X	X

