ABNAS = A-B neuropsychological assessment schedule, AE = adverse event, AED(s) = antiepileptic drug(s), β-hCG = beta-human chorionic gonadotropin (or hCG = human chorionic gonadotropin), C-SSRS = Columbia-Suicide Severity Rating Scale, eCRF = electronic case report form, EQ-5D-Y = EuroQol 5 Dimensions-Youth, fT3 = free triiodothyronine, fT4 = free thyroxine, IGF-1 = insulin-like growth factor-1, IxRS = interactive and response system, PK = pharmacokinetics, TSH = thyroid-stimulating hormone.

Table 4 Schedule of Procedures/Assessments in Study E2007-G000-311: Core Study

Phase	Pre-Treatment	Treatment Phase									Early Discontinuation ^d	Unscheduled
	Screening/Baseline	Titration ^a				Maintenance ^b				Follow-up ^{b,c}		
Visit	1	2	3	4	5	6	7	8	9			
Week	From up to -4 weeks ±3 days to Week 0 (outside of Japan) -4 weeks ±3 days to Week 0 (Japan only) (revised per Amendment 02)	0	2	5	8	11	15	19	23	27		
Procedures/Assessments												

- a: All visits to be done within ±3 days of the schedule. Each study visit is based on the actual prior visit (eg, Visit 3 is completed 2 weeks ±3 days of Visit 2, Visit 4 is completed 3 weeks ±3 days of Visit 3, Visit 5 is completed 3 weeks ±3 days of Visit 4). (revised per Amendment 02)
- b: Visit to be done within ±7 days of the schedule. Each study visit is based on the actual prior visit (eg, Visit 6 is completed 3 weeks ±7 days of Visit 5, Visit 7 is completed 4 weeks ±7 days of Visit 6, Visit 8 is completed 4 weeks ±7 days of Visit 7, Visit 9 is completed 4 weeks ±7 days of Visit 8). (revised per Amendments 02 and 03)
- c: The Follow-up Visit only applies to those subjects who complete the Core Study (or who discontinue the study early), but do not roll-over into Extension A and is to occur 4 weeks (±7 days) after Visit 9 or last dose of study drug.
- d: These assessments will be conducted for subjects who discontinue the study early for any reason after Visit 2.
- e: Physical and neurological examinations will only be performed at Visit 1 and Visit 9 and at the Follow-up Visit, and at the Early Discontinuation Visit (if applicable). For all other clinic visits during the study, the physical and the neurological exams will only be performed when there is a complaint from the subject. Clinically significant abnormal findings from the physical or the neurological examinations will be reported as AEs.
- f: Blood pressure and pulse will be taken.

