- s: Telephone interviews with the subjects and/or caregiver will be conducted 1 week after Visit 2, Visit 3, Visit 4, Visit 5, Visit 6; and at the midpoint (±3 days) between each visit from Visit 7, Visit 8 and Visit 9 to ensure that subjects are completing their seizure diaries regularly and to assess AEs, study drug compliance, and concomitant medications, including AEDs. Subjects whose dose was decreased before the scheduled telephone interview will be strongly encouraged to return to the clinic (instead of the scheduled telephone interview) for further consultation with regard to study drug administration. The site will contact IxRS to receive further dispensing instructions. Subjects will then return for their regularly scheduled visit.
- t: ABNAS to assess patient-perceived cognitive effects of AED treatment, measuring 5 aspects of cognitive function: fatigue, memory, concentration, motor speed, and reading, using a 4-point scale.
- u: To be administered twice at Visit 1 (for training purposes only).
- v: Subjects who discontinue after Week 12 must have assessments performed at the Early Discontinuation Visit.

[Table 5](#) and [Table 6](#) present the Schedule of Procedures/Assessments for Extension A and Extension B of the study, respectively. (revised per Amendment 03)

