### 5.5 Pharmacokinetic, Pharmacodynamic, Pharmacogenomic, and Other Biomarker Analyses

Perampanel plasma concentrations were obtained from blood samples drawn at any time during the treatment phase (Weeks 15, 19 and 23/EOT). Details of the analysis methods for population PK/PD modeling will not be described in this SAP but will be described in a separate analysis plan.

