**Table 1: Mapping of Study Day Ranges to Week**

Windowing Period	Study Day Range (Relative to First Dose)	Week
Pretreatment	Day $\leq 1^a$	0
Treatment	$2 \leq \text{Day} \leq 25$	2
Treatment	$26 \leq \text{Day} \leq 46$	5
Treatment	$47 \leq \text{Day} \leq 67$	8
Treatment	$68 \leq \text{Day} \leq 88$	11
Treatment	$89 \leq \text{Day} \leq 119$	15
Treatment	$120 \leq \text{Day} \leq 147$	19
Treatment	$148 \leq \text{Day} \leq 175$	23
End of Treatment(EOT) of Core Study	-	b
Follow up for completer of Core Study	$176 \leq \text{Day} \leq 203$	c
Follow up for discontinuation of Core Study	After the date of discontinuation $\leq \text{Day} \leq \text{last dose of study drug} + 35$	

- a: All assessments performed on the same date as the date of first dose were to be performed prior to dosing; results from these assessments will be regarded as Pretreatment values in the analyses.
- b: The last non-missing value measured in the Treatment Phase will be handled as the data of EOT of the Core Study. The Follow-up visit will not be included in this analysis visit.
- c For the safety assessment other than AE, the data assessed as the planned visit of the Follow-up will be handles as those of Follow-up visit. AE occurred on or after the date of discontinuation will be handles as that of Follow-up period.

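### ABNAS and LGPT are not required for children who stop before Week 12, so their end-of-treatment summaries describe only children who stayed on study past Week 12

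*Protocol*

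**What the plan says.** Protocol Table 4 (Section 9.5.2.1) places ABNAS and LGPT at Visit 1 (training only), Visit 2 (Week 0), Visit 7 (Week 15), Visit 9 (Week 23) and the Early Discontinuation (ED) Visit. On these two rows alone, the ED cell carries note v: "Subjects who discontinue after Week 12 must have assessments performed at the Early Discontinuation Visit". The ED column as a whole carries note d: "These assessments will be conducted for subjects who discontinue the study early for any reason after Visit 2".

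On timing, Protocol Section 9.1.2.1 says: "The Titration Period is a duration of up to 11 weeks". On stopping, Section 9.1.2.2 says: "Those who cannot tolerate a minimum of 2 mg dose must discontinue from the study".

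The tests serve secondary objective 2 (Protocol Section 8.2): "To evaluate the effects of perampanel on cognition, behavior, visuomotor skills, and growth and development in children". Secondary endpoint 3 is their change from baseline at Weeks 23 and 52.

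For end of treatment, note b to the study-day mapping table in Core SAP Section 8.2.2 says: "The last non-missing value measured in the Treatment Phase will be handled as the data of EOT of the Core Study". Core SAP Section 5.3.5.2 plans no special handling of missing values for these scales.

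**The concern.** Dose escalation is when a child who tolerates the drug poorly is likely to stop. Note v lifts the ED requirement for exactly that stretch, and only for the named cognitive and visuomotor tests. A child who stops for slowing or poor coordination at Week 6 can leave with a baseline score and nothing to compare it with. Nothing is imputed, so that child drops out of the change-from-baseline summaries. If such children did worse than those who stayed, the summaries look better than the truth for all treated children. Values not collected at the ED Visit cannot be recovered at analysis.

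**Working it through.** No sample-size, power or alpha figure bears on this point. The check is a reading of the schedule, a trace through the SAP rules, and a labelled illustration of size.

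**1. Where the gap lies.** Visit intervals and windows are in Table 4, notes a and b. Each visit is timed from the actual previous one, so the windows add up.

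- Visit 6, end of Titration: 14 + 21 + 21 + 21 = 77 days after Visit 2 (Week 11). Earliest 77 − (3 + 3 + 3 + 7) = 61; latest 77 + 16 = 93.
- Visit 7, first on-drug ABNAS and LGPT: 77 + 28 = 105 days (Week 15). Earliest 61 + 28 − 7 = 82; latest 93 + 28 + 7 = 128.
- Note v cut-off: 12 × 7 = 84 days.

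The uncovered stretch runs from Week 0 to Week 12: nominal Titration plus about a week. At the edges, a child whose visits run late could still be in Titration after Week 12 and would be tested on leaving. A child whose visits all run early could reach Visit 7 just before Week 12.

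**2. The same visit, test by test.**

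| Test | On-drug visits, Core | Core ED Visit | Extension A ED Visit (Table 5) |
|---|---|---|---|
| ABNAS, LGPT | Weeks 15, 23 | Only after Week 12 | No limit |
| CBCL, EQ-5D-Y, EEG | Week 23 | No limit | No limit |

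The documents give no reason for the difference.

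**3. A child who stops at Week 5, traced through the Core SAP.**

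- As written: no on-drug ABNAS or LGPT is required. If none is done, there is no end-of-treatment value and the child is absent from the change summaries.
- With an ED test: the value maps to its own day window (Days 26 to 46 are Week 5). The Week 23 window is Days 148 to 175, so it does not enter the Week 23 endpoint. It can enter the end-of-treatment row.
- Exposure-cognition analysis: the PK/PD Analysis Set needs a quantifiable concentration at a Maintenance visit (Protocol Section 9.7.1.2). This child has none, tested or not.
- Possible snag: for children who discontinue, the mapping table assigns days after discontinuation to follow-up, and note b keeps the Follow-up visit out of end of treatment. Note c ties follow-up for non-AE data to the planned Follow-up visit, which leans toward counting an ED test as treatment, but no text says so.

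**4. Size, by assumption only.** Let *p* be the proportion stopping before Week 12 and *g* how much worse their mean change is, in SD units. If the others have mean change *m*, the all-treated mean is (1 − *p*)*m* + *p*(*m* + *g*) = *m* + *pg*. The reported mean is *m*, so the understatement is *pg*. The documents give neither *p* nor *g*.

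| *p* | Children of 160 | *g* = 0.5 SD | *g* = 1.0 SD |
|---|---|---|---|
| 5% | 8 | 0.025 SD | 0.05 SD |
| 10% | 16 | 0.05 SD | 0.10 SD |
| 15% | 24 | 0.075 SD | 0.15 SD |
| 20% | 32 | 0.10 SD | 0.20 SD |

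If early leavers fared no worse (*g* = 0), there is no bias.

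**The case against.** The strongest reply has four parts.

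- **Other data cover early leavers.** The protocol lists CBCL among its cognition endpoints and requires it at the ED Visit without limit. A neurological examination, including mental status, motor and cerebellar function, is also due there. Adverse events of alertness and cognition are summarized for the Safety Analysis Set. This stands in part. A reader might infer that these children have no cognitive data at all, and the documents do not support that. But Protocol Section 9.5.1.5.7 describes CBCL as a measure of behavioral and emotional problems, and none of these sources gives a change from baseline in ABNAS or LGPT.
- **The named endpoint and the exposure analysis would not move.** This stands, as step 3 shows. A reader might infer that note v biases the Week 23 endpoint or the exposure-cognition relation. Early leavers are absent from both whatever note v says.
- **Leavers are not excluded as such.** This stands. Note v requires testing of everyone who stops after Week 12, including for intolerance, and children may stay on at a reduced dose and be tested. It is therefore wrong to infer that the tests describe only children who tolerated the drug. Nor does note v forbid earlier testing; it simply does not require it.
- **Notes d and v can be read together.** A cell-specific note ordinarily qualifies a column-wide one, and a limit on exactly two instruments may be deliberate. The first half is fair: this need not be called a contradiction. The second is conjecture. Burden is a weak explanation, since the ED Visit already includes CBCL, EEG, ECG and laboratory tests. Practice effects are no better, because note u provides two training administrations and note v sets no minimum interval: a child leaving at Week 16 is retested about a week after Week 15.

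**Conclusion.** The coverage gap is real and narrow. Children who stop before Week 12 have no required post-baseline ABNAS or LGPT, so the end-of-treatment summaries of these tests describe only children who remained on study past Week 12, apart from any test a site does unprompted and the edge cases in step 1.

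The likely direction is understatement of harm. That rests on early leavers faring worse, which is plausible but not shown: Protocol Section 9.5.5 also lists loss to follow-up, subject choice and withdrawal of consent as reasons for leaving.

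The size cannot be estimated from the documents. A reader might be tempted by a percentage. For example, suppose ABNAS worsens by 10 points in early leavers and 1 point in the others, with 5% to 15% leaving. The all-treated mean is then 0.05 × 10 + 0.95 × 1 = 1.45 to 0.15 × 10 + 0.85 × 1 = 2.35, and a reported 1.0 understates it by 1 − 1/1.45 = 31% to 1 − 1/2.35 = 57%. The 10-versus-1 contrast has no source in the documents, and the percentage is large mainly because the base is 1 point. The same gap is 0.45 to 1.35 points on a 0 to 72 scale.

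The change is worth making because it is cheap, concerns a stated safety objective, and secures values that cannot be obtained later.

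**What to change.** 1. In Table 4 note v, delete the Week 12 limit, so that ABNAS and LGPT are done at the ED Visit for every child who discontinues after Visit 2, in line with note d.
2. In Core SAP Section 8.2.2, state that an ABNAS or LGPT done at the ED Visit counts toward end of treatment rather than follow-up, and use these values in the end-of-treatment row.
3. Report the number of treated children with no post-baseline ABNAS or LGPT, with their reasons for discontinuation and their cognition TEAEs, beside the change-from-baseline summaries. If data collection is already complete, this is the only remedy left.

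The cost is one footnote in an amendment, one sentence in the SAP, one extra table, and some added test time for the few early leavers at a visit that already takes place. The change will not bring these children into the Week 23 endpoint or the PK/PD set and should not be presented as doing so.

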9.5.2.2 Description of Procedures/Assessments Schedule

The schedule of procedures/assessments for the Core Study, Extension A, and Extension B of the study are presented in [Table 4](#), [Table 5](#), and [Table 6](#), respectively. (revised per Amendment 03)

A brief description of the C-SSRS is provided in [Section 9.5.1.5.7](#).

9.5.3 Appropriateness of Measurements

All clinical assessments are standard measurements commonly used in studies of Phase 3 studies of epilepsy in pediatric subjects.

The safety assessments to be performed in this study, including hematology analyses, blood chemistry tests, urinalysis, radiologic studies, and assessment of AEs, are standard evaluations to ensure subject safety.

9.5.4 Reporting of Serious Adverse Events, Pregnancy, and Events Associated With Special Situations

9.5.4.1 Reporting of Serious Adverse Events

All SERIOUS ADVERSE EVENTS, regardless of their relationship to study treatment, must be reported on a completed SAE form by email or fax as soon as possible but no later than 24 hours from when the investigator becomes aware of the event.

SAEs, regardless of causality assessment, must be collected through the last visit (through the last visit in the Treatment Phase and for 28 days after the subject's last dose). All SAEs must be followed to resolution or, if resolution is unlikely, to stabilization. Any SAE judged by the investigator to be related to the study treatment or any protocol-required procedure should be reported to the sponsor regardless of the length of time that has passed since study completion.

The detailed contact information for reporting of SAEs is provided in the Investigator Study File.

For urgent safety issues, please ensure all appropriate medical care is administered to the subject and contact the appropriate study team member listed in the Investigator Study File.

It is very important that the SAE report form be filled out as completely as possible at the time of the initial report. This includes the investigator's assessment of causality.

Any follow-up information received on SAEs should be forwarded within 1 business day of its receipt. If the follow-up information changes the investigator's assessment of causality, this should also be noted on the follow-up SAE form.

Preliminary SAE reports should be followed as soon as possible by detailed descriptions including copies of hospital case reports, autopsy reports, and other documents requested by the sponsor.

The investigator must notify his/her IRB/IEC of the occurrence of the SAE in writing, if required by their institution. A copy of this communication must be forwarded to the sponsor to be filed in the sponsor's Trial Master File.

